## **Data analysis**

### OCT Analysis

Acceptable images should have clear and sharp focus artifacts free (e.g., motion lines), without motion artifact (identified by horizontal misalignment of vessel segments on en face images), and Scan Quality of 6 or higher. The scans will be evaluated for vessel density, vessel length per unit area, flow index, foveal avascular zone area. Capillary dropout will also be recorded, if present.

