### **Hypothesis**

Ingestion of caffeine in glaucoma patients and healthy subjects may decrease peripapillary and macular blood flow.

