## **Methods:**

### **Study Design**

Interventional Prospective Clinical Trial

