### **Procedures Involved**

Qualifying patients presenting to the Wills Eye Hospital Glaucoma Service will be asked for enrollment. Informed consent will be obtained from all participants. Subjects will undergo a comprehensive eye examination including Humphrey visual field and ocular biometry in both eyes. Scans will be obtained with the Avanti AngioVue HD OCTA (Optovue, Inc, Fremont, CA, USA), before and, one hour and two hours after a 200 mg caffeine tablet ingestion. All eyes will undergo imaging using the standard 4.5 mm HD Disc

scan protocol and the 6mm HD Retina scan protocol. In addition, a regular ONH structural scan (along with a 3D-Disc baseline scan) and a regular GCC structural scan will be acquired which provide comparison to normative database of the device to characterize the RNFL and GCC thickness status of the study eyes. Arterial blood pressure, heart rate and IOP will also be measured before and, one and two hours after the 200 mg caffeine tablet ingestion.

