## **Confidentiality**

Every effort will be made to protect the confidentiality of the data of the participants. All data will be de-identified and the assigned ID number will be used to track individual participants.

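### No masking of the scan reader to time point or diagnosis is specified, although scan acceptance is partly visual and capillary dropout is an undefined before/after outcome

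*Protocol*

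**What the plan says.** The Study Design section gives the design as "Interventional Prospective Clinical Trial". No placebo, randomisation or masking appears anywhere in the protocol. Under Procedures Involved, scans are taken "before and, one hour and two hours after a 200 mg caffeine tablet ingestion", and this applies to all four groups, healthy subjects included. The Hypothesis section expects that caffeine "may decrease peripapillary and macular blood flow".

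The OCT Analysis section sets the conditions for an acceptable scan. One is numeric: "Scan Quality of 6 or higher". The others are visual: sharp focus, no motion lines, and an image "without motion artifact (identified by horizontal misalignment of vessel segments on en face images").

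Study Data and Outcome Measures lists areas of capillary dropout or non-perfusion alongside flow index and vessel density, all assessed before dosing and at one and two hours. On how dropout is read, OCT Analysis says only "Capillary dropout will also be recorded, if present".

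The nearest text to masking is under Confidentiality: "All data will be de-identified and the assigned ID number will be used to track individual participants".

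**The concern.** Two steps appear to depend on a person's judgement: whether a scan passes the visual criteria, and whether dropout is present and how large its area is. A reader who knows that a scan is post-dose, or comes from a glaucoma patient, also knows the direction the study expects.

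In a placebo-controlled study, a reader's tendency to call more dropout on later scans would fall on both arms and largely cancel. Here the change from baseline is the only estimate of the caffeine effect. The healthy group does not help, because it takes caffeine too. The Statistical Analysis section also plans to relate blood flow differences to diagnosis, so knowledge of the diagnosis could colour that comparison as well.

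This is not a detail that an analysis plan can supply later. Masking governs how the data are generated and has to be in place before scans are read. OCT Analysis already sets the reading rules, so a masking rule belongs there.

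**Working it through.** The protocol gives no significance level, power, effect size or test for this outcome, so there is no figure of its own to reproduce. The check has two parts.

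**1. What the text does and does not cover**

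| Step | What the protocol fixes | What it leaves open |
|---|---|---|
| Scan acceptance, numeric part | Scan Quality cut-off of 6 | Nothing for a reader to decide |
| Scan acceptance, visual part | Focus and motion, with a stated sign for motion | Who judges, and whether time point or diagnosis is hidden |
| Capillary dropout | Outcome at three times, recorded if seen | Definition, grading rule, reader, masking |
| Vessel density, vessel length, flow index, foveal avascular zone area | That scans are evaluated for them | Whether software or a reader produces them |
| De-identification | Participant identity replaced by an ID number | Time point and diagnosis |

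The visual criteria apply in addition to the numeric one, so a scan scoring 6 or more can still be rejected by eye.

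**2. How few biased calls would matter (illustration only)**

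From the protocol: 4 groups of 20, so 80 participants, of whom 60 have glaucoma.

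Assumed, not in the protocol:
- dropout is called yes or no at baseline and at one post-dose time;
- the comparison is an exact McNemar test, two-sided at 0.05;
- caffeine has no true effect;
- expectation flips each absent call to present with probability q;
- no calls change in the other direction.

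*Threshold.* With k changes, all in one direction, p = 2 × 0.5^k.
- k = 5: 2 × 0.03125 = 0.0625
- k = 6: 2 × 0.015625 = 0.031

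Six changes are therefore enough. That is 6/80 = 7.5% of all participants or 6/60 = 10% of the glaucoma patients.

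*Chance of reaching it.* A call can flip to present only if dropout was absent at baseline, so the relevant number m is the count of dropout-free participants. The chance is P(Binomial(m, q) ≥ 6):

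| m dropout-free at baseline | q = 5% | q = 10% | q = 15% |
|---|---|---|---|
| 30 | 0.3% | 7% | 29% |
| 40 | 1.4% | 21% | 57% |
| 60 | 8% | 56% | 90% |
| 80 | 21% | 82% | 99% |

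*Effect of ordinary rereading noise.* With one call in the opposite direction the threshold rises: 6 against 1 gives p = 0.125, 7 against 1 gives 0.070, and 8 against 1 gives 0.039.

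**The case against.** A reader might infer that the reader is unmasked. The protocol does not say so. It does not say who reads the scans, and a separate reading procedure may exist. What can be said is that no masking is specified.

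A reader might also infer that acceptability is judged wholly by eye. It is not: the quality score is a numeric gate, and the motion criterion has a stated visible sign. That a person calls dropout is a reasonable inference, since the outcome list says only that it is detected by OCT angiography.

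The strongest objection concerns reach. The primary objective is blood flow, and dropout is one of several measures. If flow index and vessel density are software output, expectation can reach them only through which scans are kept. Nothing in the documents shows that rejecting scans for focus or motion would lower mean flow.

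The arithmetic is open to challenge too. The protocol plans no McNemar test and lists areas of dropout, not a yes/no endpoint. No baseline dropout rate is given, and with 20 moderate and 20 advanced glaucoma patients, some may already show it. The results are driven by the assumed flip rate.

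All of this stands as a limit on the size and scope of the point. It does not remove the gap: an undefined before/after outcome and a partly visual exclusion rule, with no masking specified and no comparator to absorb a reader's expectation.

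**Conclusion.** The concern holds in a limited form. As written, reader expectation in the hypothesised direction cannot be excluded for dropout calls or for visual scan acceptance.

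It would go too far to conclude that expectation alone could produce the study's whole caffeine effect. The quantitative flow measures, if automated, are exposed only through scan selection, and neither the direction nor the size of that route can be worked out from the documents.

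For dropout, the illustration shows sensitivity to a small bias, not that a bias will occur. At a 10% flip rate the chance of a nominally significant false result runs from 7% to 82% as the dropout-free number goes from 30 to 80. Over flip rates of 5% to 15% it runs from under 1% to 99%. The flip rate, the baseline count, the yes/no call, the test and the absence of reverse changes are all assumptions.

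The change is worth making because it costs little and protects the only contrast that the design offers.

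**What to change.** Add the following to OCT Analysis:

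- Scans are exported under a random code that hides participant ID, time point and diagnosis group.
- Visual acceptability and capillary dropout (presence and area, against a written definition) are judged on the coded scans, in random order, by the study's reader.
- The code is broken only after all readings are locked.
- Rejected scans are reported by time point and group, so that any uneven selection can be seen.

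Technicians may still repeat an obviously failed scan during the session.

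The cost is some recoding and shuffling of exported files, a short dropout definition and a few protocol sentences. No extra reader, scan or visit is needed, and ID coding is already planned. One limit remains: advanced glaucoma may be visible on the scan, so masking to diagnosis is only partial. Masking to time point, which matters most here, is feasible.

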### Statistical Analysis

Continuous variables will be gathered for all groups using the following statistics: the mean, standard deviation, minimum, maximum, median, first quartile, and third quartile values. The frequency and percentages will be reported for the categorical measures. Subgroup analysis will be performed to determine differences in blood flow related to the diagnosis, IOP change and ocular perfusion pressure.

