#### **Number of Patients to Enroll**

- 20 patients with early stage primary open angle glaucoma
- 20 patients with moderate stage primary angle glaucoma

- 20 patients with advanced stage primary angle glaucoma
- 20 healthy subjects without glaucoma

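### The protocol names subgroup analysis for ocular perfusion pressure, a continuous quantity, and does not say that diagnosis is accounted for; a continuous slope with enrolment group in the model would use the same data better.

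*Protocol*

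**What the plan says.** The Statistical Analysis section has a descriptive part and one comparative sentence. The descriptive part reads: "Continuous variables will be gathered for all groups using the following statistics: the mean, standard deviation, minimum, maximum, median, first quartile, and third quartile values". Frequencies and percentages are added for categorical measures. The comparative sentence is: "Subgroup analysis will be performed to determine differences in blood flow related to the diagnosis, IOP change and ocular perfusion pressure".

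That sentence puts three factors under one method. Diagnosis is a category, fixed by enrolment in Number of Patients to Enroll. Perfusion pressure is not. The protocol gives no formula for it, but its components are recorded as numbers at three times, under Procedures Involved: "Arterial blood pressure, heart rate and IOP will also be measured before and, one and two hours after the 200 mg caffeine tablet ingestion".

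The sentence gives no classes or cut-points for perfusion pressure. It does not say which of the three time points is meant, or whether diagnosis is held constant when perfusion pressure is examined.

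**The concern.** Subgroup analysis suits diagnosis, which comes in four ready-made groups. Applied to a continuous measurement it requires classes, and every subject within a class is then treated as having the same perfusion pressure. That discards information in a trial of 80 people.

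A second issue is independent of the first. The enrolment groups run from healthy to advanced glaucoma, and the factors are listed side by side with nothing said about adjusting one for another. If the groups differ both in perfusion pressure and in their response to caffeine, an analysis across all 80 subjects that ignores group will link the two even when no link exists within any group.

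At stake is one of the three relations the plan sets out to determine. The primary objective, the acute change in blood flow after caffeine, is not affected.

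**Working it through.** The protocol states no power, alpha, effect size or SD here, so there is no figure to reproduce.

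**Input from the protocol:** Number of Patients to Enroll sets four groups (early, moderate and advanced glaucoma, and healthy) at 20 each. Total N = 4 × 20 = 80.

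**Assumptions, not in the documents:** normal perfusion pressure, two-sided alpha of 0.05, the correlations, and the group gaps in within-group SD units.

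**1. Information kept after cutting**

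For two classes cut at quantile p, with c the normal quantile at p, the share kept is φ(c)² / [p(1 − p)]. At the median this is 2/π = 0.637. For k equal classes scored by their means, it is the between-class share of the variance.

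| Grouping | Kept | Lost |
|---|---|---|
| Median split | 0.637 | 36% |
| 40/60 | 0.622 | 38% |
| 25/75 | 0.539 | 46% |
| 20/80 | 0.490 | 51% |
| Tertiles | 0.793 | 21% |
| Quartiles | 0.861 | 14% |
| Quintiles | 0.897 | 10% |

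A median split of 80 subjects is worth about 80 × 0.637 = 51 subjects.

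**2. Power at N = 80**

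Fisher z approximation: power ≈ Φ(atanh(r) × √(N − 3) − 1.96). A median split shrinks r by √(2/π) = 0.798.

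- r = 0.30, continuous: atanh(0.30) × √77 = 2.716, so Φ(0.756) = 0.775, or 78%.
- r = 0.30, median split: r becomes 0.239, and atanh(0.239) × √77 = 2.142, so Φ(0.182) = 0.572, or 57%.
- r = 0.20: 43% v 29%. r = 0.40: 96% v 83%.

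Splitting within one diagnosis group instead (N = 20, so 10 v 10) gives, at r = 0.30, atanh(0.239) × √17 = 1.006 and a power of about 17%. The continuous value in one such group gives about 25%.

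**3. Confounding by diagnosis if group is left out**

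Simulation: four groups of 20, equally spaced means, no relation within any group. The gap is healthy to advanced and applies to both perfusion pressure and flow change.

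| Gap in both | Median split, no group term | Continuous, no group term | Continuous, with group term |
|---|---|---|---|
| 0.5 SD | 6% | 6% | about 5% |
| 1.0 SD | 14% | 19% | about 5% |
| 1.5 SD | 44–46% | 58–60% | about 5% |

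Ranges show separate simulation runs. If the groups differ in only one of the two variables, the rate stays at about 5%.

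Hand check at 1.0 SD: the group means are −0.5, −0.167, 0.167 and 0.5, so the between-group variance is 0.139 and the induced correlation is 0.139/1.139 = 0.122. Then atanh(0.122) × √77 = 1.075, and the two-sided rejection rate is about 19%, as simulated.

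The continuous column is higher than the split column. The confounding therefore comes from omitting group, not from cutting perfusion pressure, and only the group term removes it.

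**The case against.** The strongest reply is that the sentence is a one-line outline. It specifies no cut, number of classes, pooling or model, and such details commonly belong to a statistical analysis plan, which is not shown here. It can also be read as relating blood flow to perfusion pressure within the enrolment groups, or as loose wording for a correlation or regression. Perfusion pressure appears in neither the objective nor the hypothesis.

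Much of this stands. A reader might infer that the protocol will split perfusion pressure at its median, or that it will pool the four groups. It says neither. A reader might also take a loss of about a third as fixed, but that holds only for a two-way split near the median. Nor does the text suggest that an analyst would search for the most favourable cut, so no inflated error rate from such a search can be charged to it. Confounding requires the groups to differ in both perfusion pressure and flow change, and the documents give figures for neither.

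What does not stand is that the point is only a request for detail. The protocol names a method for this variable, and that method does not fit its scale. A later plan that followed the sentence faithfully would inherit the mismatch. If a regression was always meant, the edit makes the text say so.

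**Conclusion.** The point holds in a conditional form and is worth correcting. Subgroup analysis is the only method named for perfusion pressure, which is continuous. Followed literally, it costs about 36% of the information for a split near the median, within a range of about 10% to 51% over plausible groupings. At an assumed r = 0.30 that is a drop from about 78% to 57% power.

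The confounding risk is separate and rests on two further assumptions: that the groups are analysed together without a group term, and that they differ in both variables. The protocol's silence on adjustment makes this a possibility, not a demonstrated flaw. Under those assumptions the excess over 5% is negligible at gaps of 0.5 SD and large at 1.5 SD.

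Neither issue touches the primary comparison of blood flow before and after caffeine.

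**What to change.** In the Statistical Analysis section, reserve the word subgroup for the four enrolment groups, take perfusion pressure out of that list, and add a sentence such as:

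*The relation of OCTA change to baseline ocular perfusion pressure will be estimated as a slope with 95% CI, with perfusion pressure entered as a continuous variable in a model that also contains enrolment group.*

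Baseline is suggested because it is the time point not affected by the dose. If the sponsor means a post-dose value or a change, the sentence should say so. IOP change is also continuous, so it too should leave the subgroup list once that word is reserved for enrolment groups. How to interpret it as a post-dose measure is a separate question.

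Cost: a sentence or two, with no new data, visits or subjects. The slope assumes linearity, which needs a simple check such as a plot or a quadratic term. Enrolment group uses three degrees of freedom, taking the residual from 80 − 2 = 78 to 80 − 5 = 75.

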## **Confidentiality**

Every effort will be made to protect the confidentiality of the data of the participants. All data will be de-identified and the assigned ID number will be used to track individual participants.

